**Recruitment**

All participants will be recruited through CAMH Complex Care & Recovery inpatient forensic services. Following orientation to the study for clinical teams, clinical staff will (i) first clear involvement with the individual’s MRP and then (ii) approach potential participants who they consider appropriate using the script provided in Appendix I. Participants will then be screened by research personnel via a referral form (Appendix II) to identify any potential exclusion factors (high paranoia, primary issue of hoarding, etc.).

Potential participants who indicate further interest in hearing more about the study and provide assent to be contacted by a member of the research team will then be contacted by a member of the research team who will engage them in a written informed consent process. At that meeting, participants will be provided with a clear explanation of the objectives, procedures, rights as a research subject, risks and benefits of the study and all questions will be answered prior to obtaining their signature on the informed consent document. If a participant is incapable of providing written informed consent, a member of the research team will meet with them and their Substitute Decision Maker (SDM) and provide the same briefing as described above prior to obtaining the SDM's signature on the SDM informed consent form. If the participant has the capacity to understand the significant of the research, an assent form will also be completed with the participant. If they are not interested in participating (dissent/do not assent), these prospective participants will not be included in the study, but will be informed they will be eligible to receive CAT at a later date. A member of the research team will connect with the participant at 1-month into the study to confirm their continued assent to participate. Should the participant want to withdraw at this time they will be removed from the study and a member of the research team will ask the participant if the previously collected data may or may not be used in data analysis. Consent for audio recording during the focus group will be obtained at both consent timepoints (entry and 1-month). If a participant does not consent to have their responses audio recorded during the focus group they may choose to have an individual interview that is not recorded.

All forensic inpatients identified by their treatment team as potential CAT recipients will be given the option to participate in the research study. Participation in the study is voluntary. The decision to participate will not affect patients' receipt of usual treatment or clinical services. Participants will be informed that they have the option of terminating their participation in the study and the intervention at any time, without consequence.

A delegated Research Coordinator will access personal health information (PHI) in I-CARE to determine eligibility of clients to participate in the research study. No PHI will be collected. PHI will not be accessed until informed consent or assent is obtained. .

For participating in the 30 individual interviews following participation in the finCAT intervention, clients will receive \$10 value in gift cards from Gifts of Light or Stamp Store stamps depending on preference. Care providers will not be reimbursed for their time as focus groups will occur during work hours.

### ***Confidentiality***

Assessments will be conducted in a private space on the unit to protect any sensitive information during data collection. All participant data will be de-identified using a consecutive numeric code/study identifier (e.g. first participant enrolled, is participant 1) as soon as possible after the participant has consented into the study. A master log will be kept in a password protected file on a secure server that links participants to their numeric identifier. All study specific documents will use a participant study identifier when it is required (e.g. assessment package). The minimum PHI necessary will be collected. No participant names will be used in the dissemination of study findings.

Electronic assessment data will be stored on a secure server that is password protected and only accessible by study personnel. Hard copies of assessment data and consent forms will be stored in separate

locked filing cabinets in a locked office at CAMH. Only the Principal Investigator and CAT Clinician will have keys to the filing cabinet. A master hard copy list indicating participant names and linking numbers will be kept in a separate file from the data and stored as noted above. A backup copy of the study data will be stored on an encrypted memory stick and kept in the locked filing cabinet in the locked office. Referral forms, consent forms and assessment hard copies will all be kept in separate locked filing cabinets.

Client-specific research data gathered as part of this study may be shared and provided to the participant's unit treatment team for client care. All client data gathered will be kept confidential within the participant's treatment team and the research project team. All other gathered data (i.e. staff data) will be kept de-identified, confidential, and anonymous.

With regards to the focus group, while the study team will take precautions to protect each participant's confidentiality we cannot guarantee that other members of the focus group will respect their privacy or keep the discussions of the group confidential.

All data will continue to be securely stored and protected for the required retention period of 10 years beginning at the study's closing date. Hard copies of original study documents will be in the study binder stored in a locked filing cabinet in a locked room at CAMH. Electronic data will be reviewed at the 5 year time point to ensure integrity as required. Destruction will occur at the end of the 10 year retainment period. The research coordinator will be responsible for the storage and destruction of participant data.

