#### *Life Skills Profile (LSP)*

Personal hygiene will be measured by scores on the Life Skills Profile (LSP; Rosen, Hadzi-Pavlovic, & Parker, 1989). The LSP consists of 39 clinician-rated questions on a four-point scale and measures various aspects related to daily life activities: self-care; non-turbulence; social contact; communication; responsibility. For this project, only the self-care ratings from the full LSP-39 will be completed by service providers. Current inpatient research on the use of CAT also uses this scale as a primary measure of the effectiveness of CAT. Scores will be obtained from the nursing staff not directly involved in the delivery of the finCAT intervention.

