#### *Evidence-Based Practice Attitude Scale (EBPAS)*

The attitudes of the team members towards finCAT will be measured using the Evidence-Based Practice Attitude Scale (EBPAS; Aarons, 2004) adapted to specifically target attitudes towards CAT. The EPBAS is a self-report questionnaire consisting of 15 items measured on a 5-point Likert scale ranging from 0 ('Not at

all’) to 4 (‘To a very great extent’) and consists of four subscales: (1) appeal, (2) requirements, (3) openness and (4) divergence.

*Essen Climate Evaluation Schema (Essen CES)*

The therapeutic alliance on the unit will be measured by clinician and client ratings on the Essen Climate Evaluation Schema (Essen CES; Schalast et al., 2008). The Essen CES is a 15-item questionnaire measured on a 5-point Likert scale ranging from ‘Not at all’ to ‘Very Much’ and consists of three subscales: (1) Patient’s Cohesion, (2) Experienced Safety, and (3) Therapeutic Hold. For this study, client and clinician ratings on the Therapeutic Hold subscale will be collected.

[figure not shown]
*Qualitative Care Provider & Participant Attitudes*

The attitudes of the team members and participants towards finCAT will also be measured using a qualitative feedback form created for this study. Questions will target attitudes towards finCAT, perceptions of the impact of finCAT, and perceptions of team tension or conflict arising or abating during the implementation of finCAT. Small focus groups with healthcare providers and individual interviews with interested clients will be facilitated by student investigators. Interviews will be audio-recorded and transcribed verbatim.

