#### Individual Interview Questions for Clients

- 1. How do you feel finCAT has influenced, if at all, your room organization on the unit?
  - a. What improvements did you notice about your room?
  - b. Do you think there is more room for improvement?
- 2. How do you feel finCAT has influenced, if at all, your self-care on the unit?
  - a. What improvements related to self-care (e.g., personal hygiene) do you feel you've had?
  - b. Do you think there is more room for improvement?
- 3. How did you feel during the finCAT sessions?
  - a. What made you feel that way?
- 4. What did you enjoy about finCAT?
- 5. What did you not enjoy about finCAT?
- 6. How did you find finCAT influenced your relationships with clinicians on the unit?
- 7. Any additional thoughts or comments that you would like to share?

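### The rule allowing client research data to go to the treatment team makes no exception for clients' ratings of staff or interview answers about them, which puts the candour of those answers at risk

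*Combined protocol and SAP*

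**What the plan says.** The rule is in the Confidentiality section: "Client-specific research data gathered as part of this study may be shared and provided to the" client's own care team on the unit, for the purpose of care. The next sentence places the treating team inside the boundary for client data: "All client data gathered will be kept confidential within the participant's treatment team and the research project team". Staff data are treated differently: "All other gathered data (i.e. staff data) will be kept de-identified, confidential, and anonymous". The same section says that electronic assessment data sit on a "secure server that is password protected and only accessible by study personnel", and it limits the filing-cabinet keys to the principal investigator and the CAT Clinician.

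Two client measures concern the staff themselves. Under Measures, Essen CES, "client and clinician ratings on the Therapeutic Hold subscale will be collected"; Table 3 schedules this at Baseline and Follow-Up. The client interview in Appendix III asks "How did you find finCAT influenced your relationships with clinicians on the unit", and also asks what the client did not enjoy.

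On the LSP, the Measures section says: "Scores will be obtained from the nursing staff not directly involved in the delivery of the finCAT intervention". Table 3 schedules the LSP at Baseline, Pre-CAT, Post-CAT and Follow-Up, and Data Analysis lists it among the primary variables (printed as LPS). Staff Procedures counts registered nurses among treatment team staff.

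**The concern.** The permission is broad enough to return a client's view of the staff to those staff. Clients here depend on the team: the Background ties their length of stay to review board proceedings and risk management, and under Recruitment it is clinical staff who approach them about the study. A client who knows that the team may see the answers has an evident reason to be kind about the team and the programme.

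This bears on what the study is for. Its first hypothesis includes acceptability to patients, and the interviews are the main place where clients say whether they found finCAT acceptable. The staff, speaking about clients and colleagues, are promised anonymity. The clients, speaking about staff, are not promised it against the treating team.

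The lesser concern is the LSP. The recipients whom the rule allows include the pool from which LSP raters come, so prior scores or clutter ratings could be in a rater's mind at the next rating. For the Clutter Image Rating Scale (CIRS) the protocol uses two blinded raters, so it treats rater knowledge as something to control, yet nothing comparable covers the LSP.

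**Working it through.** No power or precision figure is stated for these measures, so the check is mainly a comparison of sections. The one figure that can be reproduced is the sample size: 4 units × 6 participants = 24.

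**1. What the permission covers.** It reaches client-specific data without naming instruments. Client Therapeutic Hold ratings and individual interviews are client-specific, so they fall within it. Coding by study number does not help, because data passed on for a client's care must be linked to that client to be of use.

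**2. Whether another section narrows it.** Measures, Recruitment, Staff Procedures, Safety Protocol and the appendices contain no exclusion of Essen CES ratings, interview content or prior LSP scores. The storage sentence and the cabinet-key rule govern custody; the sharing sentence permits disclosure. The section does not say which prevails.

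**3. How much data is in reach** (Table 3, full enrolment, no dropout):

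- Client Therapeutic Hold: 2 of 2 time points, at most 24 × 2 = 48 ratings.
- Client interviews: all of them, held once at the end with interested clients.
- LSP: 4 time points, of which 4 − 1 = 3 follow an existing score (Pre-CAT, Post-CAT, Follow-Up), at most 24 × 3 = 72 ratings.

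**4. Direction of possible bias.**

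- Client answers: the incentive runs towards favourable answers. It needs only the client's awareness that staff may see them, so holding interviews at the end does not remove it.
- LSP: two mechanisms pull in opposite directions. A rater who anchors on a prior score moves the new rating towards it, which shrinks pre/post change. A rater who expects improvement moves the rating away from it, which enlarges change. The protocol gives no standard deviation, expected change or other basis for deciding between them or sizing either.

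**5. What withholding costs in time.** From Study Design Overview, Follow-Up comes two months after the end of four weeks of treatment. Post-CAT scores would be held for about 2 months, and Pre-CAT scores for about 4 weeks + 2 months ≈ 3 months. Baseline scores would be held somewhat longer, most of all on the second pair of units, where Pre-CAT comes some weeks after Baseline.

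**The case against.** The strongest reply is that a permission is not a plan. The sentence says that data may be shared and ties this to client care. Nowhere does the protocol say that Essen CES ratings, transcripts or LSP scores will be passed on, and the storage rules point the other way. Student investigators run the interviews. This stands in part: a reader might infer that exposure will happen, or will happen while the study is running, but the text establishes neither. It does allow both.

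Second, the incentive depends on what clients are told, and the consent forms are not among the material available. That stands, and it is why the point is stated as a risk. It is also a reason to settle the wording, since consent must follow whatever rule the protocol sets.

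Third, Essen CES is listed as neither a primary nor a secondary variable, and favourable answers at both time points would partly cancel in a change score. Both are fair. The interviews, however, have no baseline against which to cancel, and their transcripts are to be thematically analysed.

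Fourth, LSP nurses already know about the intervention, can see the rooms, are told clients' goals and strategies, and may have given the prior scores themselves, because rater continuity is not stated. Goal attainment is scored by consensus with the case manager, so the care team partly knows it anyway. This stands, and it makes the LSP part minor: withholding scores closes one avoidable route but does not blind the nurses.

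**Conclusion.** The point holds as a gap in a stated rule. The sharing permission has no exception by instrument or time, it covers clients' ratings of staff and interview answers about them, and it conflicts on its face with the restriction to study personnel. The consequence is a risk of favourable bias in the client acceptability and unit-climate data. It could affect both Therapeutic Hold time points and every client interview, and its size cannot be estimated from the documents. The conclusion assumes that clients know, or suspect, that staff may see their answers.

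For the LSP, the same rule could expose raters to prior scores at three of four time points, but the added effect may be small. A reader might infer that the LSP comparison therefore carries an inflated false-positive rate and try to attach a figure to it. The documents do not support that: the direction is open, anchoring on a prior score would work against finding change, and no shift size can be derived. No such figure should be quoted. Nothing here calls for a change in sample size, and in a single-group feasibility study that describes itself as underpowered, the matter is worth correcting but does not undermine the design.

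**What to change.** Amend the Confidentiality section as follows:

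- Client Essen CES ratings and client interview content are not given to the treatment team, except where safety requires it. Clients are told this at consent.
- LSP raters are not shown a participant's prior LSP scores or CIRS ratings until that participant's Follow-Up is complete.
- CAT plans, goals and safety information may still be shared at any time, since the intervention relies on the team knowing them.
- The sharing sentence and the sentence restricting electronic assessment data to study personnel are reconciled, so that it is clear who may receive what.

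This is a cheap improvement: protocol and consent wording only, with no added visits, instruments, staff or participants. The downside is that LSP raters receive these scores about two to three months later than they otherwise might.

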### ***Staff Procedures***

Allied health staff will be recruited from their respective units. If they verbally consent to participate in the research project, allied staff will complete the staff consent form with the research assistant. Allied staff will be invited to participate in an interactive workshop to facilitate their use of CAT strategies with clients participating in the research project, pre and post measures, and a focus group following the end of the intervention. Following the research study, allied health staff will be supported to continue the delivery of CAT on their units through a CAT Community of Practice.

Other treatment team staff (i.e. RNs) will be invited to participate in brief education sessions to familiarize them with CAT. Interested parties will also be invited to complete the Essen CES and staff focus groups. If they agree to participate in these measures, they will complete the staff consent form with the research assistant.

### ***Safety Protocol***

A CAT Clinician will be providing direct care to inpatient forensic clients with the support of Unit Champions who are familiar with both the client and the unit milieu. All CAT Clinicians and investigators will check in with the treatment team immediately prior to each interaction with inpatient clients and wear a personal alarm according to unit protocols. Investigators will make best efforts to meet with clients with Unit Champions. Student investigators will be accompanied by study or unit staff in all interactions. CAT interventions will in no way involve taking clients off the unit, and all investigators will exercise AWOL caution at unit entry points.

All environmental support supplies provided to clients will align with individualized unit policies and procedures, including but not limited to restrictions of no metal, no glass, no sharp objects, and no long ropes/strings. All items provided will be items participants could potentially purchase independently.

Research personnel may withdraw a participant from the study early if the researchers do not think it is in the participant's best interest to continue. Research personnel will discuss the reasons for the withdrawal with the participant. The study doctor may also end a participant's involvement in the study early, without their consent, for reasons such as:

- The study intervention does not work for them
- The participant is unable to tolerate the study intervention
- The participant is unable to complete all required study procedures

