**And**

## **(2) What are the attitudes of inpatient forensic occupational therapists and clinical teams towards implementing finCAT on their units?**

### **Methods**

#### ***Study Design Overview***

This study will expand on our preliminary work at CAMH. The study will be implemented on four CAMH general security forensic inpatient units. There will be four weeks of CAT Clinician--delivered treatment focusing on two goal areas – room organization and personal hygiene, followed by two months of maintenance by CAT Unit Champions with pre, post, and two-month follow-up, as well as project-end evaluations. In the first four weeks, we will conduct a trial of finCAT for two of the four inpatient general forensic units, followed by two months of finCAT maintenance with Unit CAT Champions supported by the CAT Clinician. This process would then be repeated on the remaining two general units at CAMH. Previous implementation of CAT has demonstrated gains within one-month; however, follow-up assessments were not conducted to determine if gains were maintained over time. While brief, this time period (i) reflects the intent of this study as a pilot test of feasibility and, (ii) aligns with this circumscribed version of CAT (as compared to the more comprehensive community version with broader outcome domains). Data will be collected from both primary participants (inpatients) and the clinical team.

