### **Measures**

#### *Clutter Image Rating Scale (CIRS)*

Room organization will be measured by ratings on the Clutter Image Rating Scale (CIRS; Frost et al., 2008). The CIRS is a 9-picture visual analogue scale used to quantify and standardize the amount of clutter in 3 different living spaces (kitchen, living room, and bedroom). For this project, only the bedroom rating scale will be utilized. The CIRS is used to measure the severity of clutter in compulsive hoarding. It has been shown to be less affected by an over-reporting bias and to have strong inter-observer reliability with a strong participant/experimenter correlation. Before and after photos will be taken of each participant's room. These photos will be rated by 2 blinded student investigators with the mean rating taken.

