#### *Goal Attainment Scaling (GAS)*

Goal Attainment Scaling (GAS) will be employed as a sensitive measure of progress on individually defined goals. GAS has demonstrated good reliability and validity with severe mental illness populations (Hurn et al., 2006). Goal attainment scaling involves the setting of 3-5 goals, each operationalized on a 3-point scale. Goals are individualized to the client and assessment of progress is determined through consensus of the clinician and case manager.

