**Data Analysis**

For this analysis, primary variables are CIRS, GAS, and LPS scores. Secondary variables are the EBPAS and additional qualitative measures of care provider attitudes.

The data analysis is as follows: (1) A descriptive profile of demographic and baseline data will be developed; (2) We will develop a descriptive profile of session attendance; (3) We will compare pre/post/follow-up measures within treatment groups using ANOVA with posthoc analyses to determine change between time points. Cohen’s d will be used to assess effect size. For all analyses  $p < .05$  will be used as the level of significance.

Transcripts from focus groups and individual interviews will be thematically analyzed using a content analysis strategy as articulated by Hsieh & Shannon, 2005. The analysis will be validated through the use of 2 independent coders and full team reviews of code summaries.

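### Participants may be removed from the study because finCAT is not working, and nothing keeps them assessed or analysed; the likely bias is small and cheap to prevent

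*Combined protocol and SAP*

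**What the plan says.** The Safety Protocol gives two routes to early removal by the study team. Under the first, "Research personnel may withdraw a participant from the study early" on best-interest grounds. Under the second, the study doctor may end a participant's "involvement in the study early, without their consent, for reasons such as" three listed items, the first being "The study intervention does not work for them". The rule is permissive, and what it ends is study involvement; it does not separate stopping finCAT from stopping assessment.

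Other sections bear on what happens next:

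- **Assessments, Table 3** schedules CIRS, GAS and LSP at Pre-CAT, Post-CAT and Follow-Up, but does not say whether they continue after early removal.
- **Data Analysis** states: "We will compare pre/post/follow-up measures within treatment groups using ANOVA with posthoc analyses to determine change between time points". It names no analysis set and no missing-data rule.
- **Recruitment** has the only rule on the data of people who leave. It covers participants who themselves choose to withdraw at the 1-month check, and concerns only data already collected.
- **Participants** sets 24 participants (6 on each of 4 units), expects minimal attrition without giving a number, and calls the sample underpowered.
- **The Proposed Project** says the results will guide future trials on drop-out and powering.

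**The concern.** The trigger for removal is the outcome under study. If people judged not to be benefiting leave and are no longer rated, or their existing scores are left out, the remaining group looks better than the group that started. There is no control arm in which to see or offset this, and the direction is known. Unlike sampling error, it does not show in a confidence interval.

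Two stated outputs would be affected. The estimated gain feeds the powering of later trials, so an inflated gain gives trials that are too small. Drop-out is itself a feasibility result, and a removal because finCAT was not working tells planners something different from a discharge or a refusal; the plan does not ask for that breakdown.

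The point is confined to removal for non-response. It does not concern best-interest, tolerability or participant-initiated withdrawal.

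**Working it through.** **Inputs from the plan.** n = 4 × 6 = 24, which reproduces the stated total; significance level 0.05, taken as two-sided. The plan gives no power figure. For 24 paired changes, power is 65% at a standardised change of 0.5 and 80% at 0.60, in keeping with the plan's own description of the sample.

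**Assumptions (not in the documents).** Normal scores with SD 1; within-person correlation 0.5, so the SD of change is √(2 − 2×0.5) = 1; completers analysed; k = 1, 2 or 4 people removed for non-response; the judgement of response correlates c with true Pre-to-Post change.

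**Bias.** Dropping the k lowest of 24 on a score correlated c with change shifts the completers' mean change by

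bias = c × (sum of the k most extreme expected normal order statistics) / (24 − k).

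For n = 24 these order statistics are 1.948, 1.503, 1.239 and 1.041 in absolute value. At c = 1:

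- k = 1: 1.948/23 = 0.085
- k = 2: 3.451/22 = 0.157
- k = 4: 5.731/20 = 0.287

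The SE of mean change is 1/√24 = 0.204, with 95% half-width 2.069 × 0.204 = 0.42.

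| c | Bias in SD, k = 1 / 2 / 4 | Bias as share of SE | ANOVA false-positive rate |
|---|---|---|---|
| 0.25 | 0.02 / 0.04 / 0.07 | 10% / 19% / 35% | 4.9% / 5.2% / 5.8% |
| 0.5 | 0.04 / 0.08 / 0.14 | 21% / 38% / 70% | 5.2% / 6.2% / 8.6% |
| 1 (bound) | 0.085 / 0.157 / 0.287 | 41% / 77% / 140% | 7.1% / 11.1% / 23.7% |

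The false-positive rates come from 40,000 simulated studies with no true change, using a one-way repeated-measures ANOVA on completers. A paired t-test on the single Pre-to-Post contrast is more sensitive: 7.0% at k = 2, c = 0.5, and 14.9% at k = 2, c = 1. At c = 0.5 the paired 95% interval covers 94.4% / 92.9% / 89.5%. With a within-person correlation of 0.7 the ratios of bias to SE are unchanged.

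**Which c is plausible.** It differs by outcome. For CIRS, "These photos will be rated by 2 blinded student investigators with the mean rating taken". For LSP, "Scores will be obtained from the nursing staff not directly involved in the delivery of the finCAT intervention". Both weaken the link between a removal decision and the score. For GAS, "assessment of progress is determined through consensus of the clinician and case manager", so the link may be closer. The value c = 1 would need change to be known exactly and is a theoretical bound only.

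**Timing.** "There will be four weeks of CAT Clinician--delivered treatment focusing on two goal areas", and Post follows directly.

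- *Removal before Post* could rest only on an impression of response, and the Post score is lost. At c = 0.5 a mixed model on the available data still leaves 0.03 / 0.06 / 0.11 of the 0.04 / 0.08 / 0.14 SD, because the Pre score predicts only part of the missing change.
- *Removal after Post* leaves both scores in hand. Using them makes the Pre-to-Post bias 0.00. The Follow-Up score is still lost. If only completers are analysed, Post-to-Follow-Up change shifts by −0.02 / −0.04 / −0.07 SD at c = 0.5, so maintenance looks slightly worse.

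**Planning consequence.** For a true standardised change of 0.5, a paired design needs 34 for 80% power. Adding the c = 0.5 bias gives 0.542 / 0.578 / 0.643, for which 29 / 26 / 21 appear to suffice; against the true 0.5 those sizes have about 74% / 69% / 59% power. This holds the SD at 1. Removal also narrows the observed SD, so the average simulated Cohen's d is 0.57 / 0.62 / 0.70, against 0.52 with nobody removed. For scale, sampling error alone spreads an estimate of 0.5 over about 0.5 ± 0.42, that is 0.08 to 0.92.

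**The case against.** The strongest reply is that the harm depends on several things the documents do not establish. The doctor must use a permissive rule for this reason, before Post or with collected scores set aside; the judgement must track the score; and completers alone must be analysed. Attrition is expected to be minimal, so four removals is a stretch. Four weeks gives little basis for a verdict of non-response, and no section says existing scores would be discarded. Without a control arm, change cannot be attributed to finCAT anyway, and no go/no-go rule hangs on the p-value. All of this stands, and it is why the point is minor.

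It can also be said that the real gap is the missing analysis set and missing-data rule, which affects every kind of attrition. That is fair, and a general rule would cover part of this. It would not cover all of it: here the plan itself authorises removal on the outcome, and when removal precedes Post an analysis rule alone recovers only a small part of the bias.

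Three limits also stand. Normal scores are a rough stand-in for a nine-picture rating and three-point goals. The remedy is weakest for GAS, where selection may be strongest. Whether present consent covers further room photos cannot be checked, because the consent pages are not in the public document.

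**Conclusion.** The concern holds, as a minor one. A stated rule permits removal from the study for non-response, and no section available keeps those people assessed or analysed. At 1 to 2 removals with c between 0.25 and 0.5, Pre-to-Post change is inflated by 0.02 to 0.08 SD, which is 10% to 38% of one standard error. At 4 removals and c = 0.5 it reaches 0.14 SD; with near-perfect selection it would no longer be small. It is zero if the rule is never used for this reason. These figures rest on the assumed number of removals, the assumed correlations and a completers-only analysis, none of which the plan states. Sampling error at n = 24 remains the larger limit on what the study can say about powering.

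**What to change.** Leave the decision to stop finCAT, and the best-interest, tolerability and consent or assent protections, unchanged. Add:

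1. **Safety Protocol:** stopping finCAT because it is judged not to work does not by itself end assessment. The scheduled CIRS photo and nurse-rated LSP at Post and Follow-Up continue while the person remains on the unit and consent or assent stands. GAS is collected where the clinician and case manager can still score it jointly.
2. **Data Analysis:** everyone who starts finCAT is analysed using all collected observations, for example in a mixed model, except data a participant asks not to be used under the Recruitment section.
3. **Reporting:** withdrawals are tabulated by reason and timing as a feasibility outcome.

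The cost is a few sentences plus a small number of extra photos and staff ratings, which ask the patient to perform no task. An ethics amendment may be needed if present consent does not cover them. The estimated effect may come out smaller.
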